6.2. Pregnancy reporting

If a participant becomes pregnant during the study, they will notify a member of the research team who will report it to the PI and note it on a CRF.

All pregnancies within the trial should be reported to the Chief Investigator and the Sponsor using the relevant Pregnancy Reporting Form within 24 hours of notification.

- Pregnancy is not considered an AE unless a negative or consequential outcome is recorded for the mother or child/foetus. If the outcome meets the serious criteria, this would be considered an SAE.
- If a participant becomes pregnant during the study and they are in the SNMES intervention group, they will stop using the SNMES for the remainder of their time in the study. Follow-up data will continue to be collected.

6.3. Device Deficiencies

A log will be kept of all of the issues and deficiencies with the electrical stimulation units, electrodes, and leg braces (knee immobiliser and AFO).

Deficiencies and issues will be fed back to the company that designed the electrical stimulator, electrodes, knee immobiliser, or AFO.

6.4. Overview of the Safety Reporting Process

The CI has the overall safety reporting oversight responsibility. The CI has a duty to ensure that safety monitoring and reporting is conducted in accordance with the sponsor's requirements.

STIM-STROKE Protocol v1.0 30-04-2025

IRAS ID: 332116 Page **52** of **70**

6.5. Responsibilities

Process for SAE

- 1. SAE identified
- 2. SAE CRF completed by a member of the research team
- 3. SAE CRF is sent to the local PI
- 4. Local PI will assess SAE for severity and causality and notify the CI of the SAE
- 5. The Sponsor will be made aware of the SAE within 24 hours of knowledge of the event via a member of the research team

Research practitioner

- Collecting data at study visit (Visit 2, 3, 4) regarding AE, AR, and SAE
- Reporting any AE, AR, SAE on the respective CRF
- Sending SAE CRF to local PI for evaluation

Principal Investigator (PI):

- Checking for SAEs when participants attend the study visit.
- Using medical judgement in assigning seriousness and causality.
- Ensuring that all SUSARs are recorded and reported to the sponsor within 24 hours of becoming aware of the event and provide further follow-up information as soon as available
- Ensuring that SUSARs are chased with Sponsor if a record of receipt is not received within 2 working days of initial reporting.

Chief Investigator (CI):

- Clinical oversight of the safety of study participants, including an on-going review of the risk / benefit.
- Immediate review of all SUSARs.

Sponsor:

- Central data collection and verification of adverse events according to the trial protocol onto a database.
- Using medical judgement to assign the SAE's seriousness and causality where it has not been possible to obtain local medical assessment – UHD Clinical Director for Research.
- Reporting safety information to Research Steering Group.
- Expedited reporting of SUSARs to the REC within required timelines.

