[name]	Protocol development, research methodology, research background, dissemination, patient and public involvement strategy	
[name]	Protocol development, research methodology, background, dissemination, patient and public involvement strategy	
[name]	Protocol development, research methodology, dissemination	
[name]	Research methodology, development of health economics	
[name]	Research methodology, development of statistical approach	
[name]	Protocol development, research methodology, research background, dissemination	
[name]	Patient and public involvement strategy	

STIM-STROKE Protocol v1.0 30-04-2025

IRAS ID: 332116 Page **13** of **70**

viii. KEY WORDS

Stroke, electrical stimulation, motor recovery, lower limb,

ix. TRIAL FLOW CHART

Patient flow through the trial is described in Figure 1 below.

Figure 1 Trial Flow Chart

STIM-STROKE Protocol v1.0 30-04-2025

IRAS ID: 332116 Page **14** of **70**

Screening and Consent

Patients within two weeks of stroke will be screened by research practitioner and therapy team for eligibility (> 18 y/o, within 2-weeks of stroke, NIHSS score of ≥ 3 for the lower limb, unable to walk (with or without AD).

Patients that meet the eligibility criteria will be provided with a PIS and study introduction.

Informed consent or consultee consent will be obtained for those that want to take part.

Do not meet eligibility criteria or decline to participate (reason logged with permission)

NIHSS- National Institute of Health Stroke Scale

AD- assistive device

MRS - Modified Rankin Scale

NPRS – Numerical Pain Rating Scale

VAS – Visual Analogue Scale (pain)

[figure not shown]
30 SCSST – 30 Second Chair Sit-Stand Test

EQ-5D-5L - EuroQOL

SNMES- surface neuromuscular electrical stimulation

Baseline Assessment (Visit 1)

Demographic and stroke information, Trunk Control Test, MRS, NPRS, VAS< dynamometer (strength), limb circumference, 30 SCSST, EQ-5D-5L, Barthel Index, Nottingham Sensory Assessment.

Visit 2, 6 weeks Follow up

Dynamometer (strength), limb circumference, 30 SCSST, EQ-5D-5L, NPRS, VAS, Barthel Index, Nottingham Sensory Assessment, resource use questionnaire

Visit 3, 12 week Follow up

Dynamometer (strength), limb circumference, 30 SCSST, EQ-5D-5L, NPRS, VAS, Barthel Index, Nottingham Sensory Assessment, 10 Metre Walk Test, resource use questionnaire. SNMES group return stimulators.

Visit 4, 6 month Follow up - END OF STUDY

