5. TRIAL PROCEDURES

Following completion of the baseline measures, individual participant randomisation will take place. Participants will be randomised to either the intervention group to receive SNMES alongside their usual care or to the control group to receive usual care alone. Participants in both groups will continue to receive their usual care and both will take part in study assessments.

Intervention group

SNMES treatment will be started within two weeks of stroke, and within 4 days of randomisation, to account for randomisation on a Friday and starting the intervention the following week. SNMES will be targeting only the weakened stroke-affected leg muscles of the thigh (hamstring, quadriceps, triceps surae) and calf (anterior tibialis, gastroc soleus). The SNMES intervention will be delivered alongside and in addition to usual care.

Treatment with SNMES is provided using a commercial constant current 2-channel battery operated electrical stimulation device and is designed in line with previous evience. ¹³

Participants receiving SNMES will be provided with

- SNMES stimulator unit
- Knee immobiliser brace
- Ankle foot orthosis

STIM-STROKE Protocol v1.0 30-04-2025

IRAS ID: 332116 Page **24** of **70**

- 4 large electrode pads
- 4 small electrode pads
- An extra 9 volt battery
- SNMES diary (in the format of their choice, written or digital)

The treating clinician will teach the participant and their family/caregivers how to use the knee and ankle braces, apply the electrodes, set up the stimulator, carry out stimulation, remove the electrode pads, and storage of the electrode pads and stimulation devices. Participants and caregivers will be provided with an instructional booklet containing written information and videos about how to use the electrical stimulation unit, electrodes, trouble shooting, and when to stop electrical stimulation. Participants and caregivers will also be provided with a diary to track their stimulation sessions and reasons for not doing a session.

The general procedure that will be used on each muscle/joint is described below.

[figure not shown]
- 1. The motor points for the appropriate muscle will be identified by the therapist. The therapist will mark this spot on the skin with a permanent marker for future sessions. This will help to ensure consistent stimulation.
- 2. The gel electrode is placed on the muscle motor point of the weak leg (stroke affected leg). Please see the images below.

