All participants will complete follow up assessments at 6-weeks (Visit 2), 12-weeks (Visit 3) and 6 months (Visit 4) after randomisation. These assessments will be administered by research practitioners and take place at the trust in which the participant was admitted for their stroke (UDH or the second site). If the participant is not able to walk or completes transfers by hoist the assessment can be carried out in the community at their place of residence. Research team members that undertake assessments in the participant's place of residence and will follow lone working policies associated with the trust.

Follow up Assessments

A summary of the study baseline and follow up assessments are in Section 5.5 and 5.6 as well as in Table 2 in Section 5.6.

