5.3. Randomisation

Once individuals/their consultees have consented to take part in the study and their baseline outcome measures have been completed the participant will be randomised in a 1:1 ratio, stratified by site to receive either SNMES or usual care via REDCap.

The randomisation sequence using random permuted blocks will be generated by a statistician outside of the trial team and implemented using a centralised independent webbased randomisation system set up within REDCap.

STIM-STROKE Protocol v1.0 30-04-2025

IRAS ID: 332116 Page **37** of **70**

The PI at the respective site or other trained clinician (on the delegation log) will undertake randomisation. This will allow the research practitioner doing the study assessments every attempt to be blinded to group allocation.

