5.4. Blinding

Participants will not be blinded to group allocation as they will know if they are receiving SNMES or usual care on its own. Participants will be educated to not disclose their intervention group to the individual who is doing their study assessments,

Clinical teams will not be blinded to the participants group allocation as the clinicians will be supporting the participants to use SNMES.

Every attempt will be made to blind research practitioners doing the outcome assessments. To explore blinding, research practitioners doing the outcome assessments will make a guess as to which group the participant was in at Visit 3 (described below). Research

practitioners will record if they were unblinded to group allocation and how this happened (e.g. saw the equipment, participant told them). The findings from this feasibility study will inform the design and blinding strategy of the subsequent definitive trial.
Have you been unblinded? Yes, No
If yes

Disclosed

Observed equipment

Other

Guess which group the participant was in – control or intervention

Rationale – free text

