5.6. Trial assessments

Trial assessments will take place at baseline (Visit 1), 6-weeks after baseline (visit 2), 12-weeks after baseline (Visit 3), and 6-months after baseline (Visit 4). Please refer to Table 2 below for details regarding what data is collected at each visit.

Data at each visit will be collected by the research practitioner who is trained in carrying out each assessment and is documented in the delegation log.

The assessment window for Visit 2 is +/- 3 days to account for the weekend in which research practitioners would not be working. The assessment window for Visit 3 and visit 4 is +/- 7 working days. It is not expected that at Visit 3 or Visit 4 there will be rapid changes in function thus the longer assessment window.

Please see Appendix 3 for complete details and instructions for how to complete each assessment.

STIM-STROKE Protocol v1.0 30-04-2025

IRAS ID: 332116 Page **39** of **70**

Table 2 Schedule and Rationale of Assessments

Measure	Brief Description	Screening	Visit 1 (baseline)	Visit 2 (6- weeks) (+/- 3 days)	Visit 3 (12 - weeks) (+/- 7 days)	Visit 4 (6 months) (+/- 7 days)
NIH Stroke Scale (NIHSS)	Assess leg strength and ability of the stroke affected leg.	Х				
Trunk Control Test (unsupported sit)	Assesses trunk control, trunk strength, and unsupported sitting balance. There is evidence that better trunk control/sitting balance is associated with return to walking.		Х			
Walking ability	Assessment of if the person can walk without support. Participants will be included if they need support and help to walk.	Х				
Modified Rankin Scale	Assesses function and ability/disability after stroke.		Х			
Numerical Pain Rating Scale	Assessment of pain, rating scale from 0 no pain to 10 extreme pain in the stroke affected leg.		Х	X	Х	Х

Measure	Brief Description	Screening	Visit 1 (baseline)	Visit 2 (6- weeks)	Visit 3 (12 - weeks)	Visit 4 (6 months)
				(+/- 3 days)	(+/- 7 days)	(+/- 7 days)
Dynamometer	Assess the strength of muscles of the thigh and calf (Quadriceps, hamstrings, gastroc soleus, and anterior tibialis).		Х	Х	Х	Х
Oxford Grading Scale/Medical Research Council Scale	Measure of strength of the lower limb rating from 0/5 no muscle activity to 5/5 full strength against resistance.		Х	Х	Х	Х
30 second chair sit-stand test	Number of sit-to stands and stand-to sits in 30 seconds, this assesses functional ability, lower extremity muscle power, and muscles endurance.		Х	Х	X	Х

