13. APPENDICIES

13.1. Appendix 1: Risk

\boxtimes $A \equiv Comparab$ \square $B \equiv Somewhat$	_			
occupational thera has been incorpor guidance IPG278	apy. The use of ele rated into clinical gu "Functional electric	ed as part of standard or usual pracectrical stimulation has been recomruidelines e.g. NICE guidelines such cal stimulation for drop foot of centra Clinical Guideline for Stroke" publish	mended as best pra as Interventional p al neurological origi	rocedures
What are the key therapeutic interveto monitor in this to	entions you plan	How will these risks be minimised	?	
IMP/Intervention	Body system/Hazard	Activity	Frequency	Comment s
Skin irritation at electrode site	Integumentary system	Participant and health care team education on monitoring skin integrity and to report any changes in skin integrity to the research team. The research team will assess the skin integrity and act accordingly to the participants. Hypoallergenic electrodes can be provides if a participant has a skin irritation as well as using a larger electrode.	Healthcare team education session. Initial session of SNMES, check at Visit 2 (week 6) and Visit 3 (week 12)	
Muscle fatigue	Musculoskeletal system	Participant and health care team education on muscle fatigue signs and symptoms. Participants will be instructed to report any muscle fatigue to the research team. The research team will assess the muscle fatigue and act accordingly to the participants symptoms. The intensity of the stimulation can be reduced which will reduce the workload on the muscle.	Healthcare team education session. Initial session of SNMES, check at Visit 2 (week 6) and Visit 3 (week 12)	
Delayed onset muscle	Musculoskeletal system	Participant and health care team education on DOMS signs and symptoms. Participants will be instructed to report any DOMS	Healthcare team education session.	

Page **68** of **70**

STIM-STROKE Protocol v1.0 30-04-2025

IRAS ID: 332116

soreness (DOMS)		to the research team. The research team will assess the DOMS and act accordingly to the participants symptoms. The intensity of the stimulation can be reduced which will reduce the workload on the muscle.	Initial session of SNMES, check at Visit 2 (week 6) and Visit 3 (week 12)

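### The role that Section 5.4 tries to blind is also assigned adverse-reaction collection, and nothing shields it from electrode marks or stimulator return, so avoidable unblinding is likely enough to need fixing

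*Protocol*

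**What the plan says.** **The commitment.** Section 5.4 states: "Every attempt will be made to blind research practitioners doing the outcome assessments". Section 5.3 has the site PI or another trained clinician perform randomisation, and gives the reason: "This will allow the research practitioner doing the study assessments every attempt to be blinded to group allocation".

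**Who does what at follow-up.** On the follow-up visits, Section 5 says: "These assessments will be administered by research practitioners". Section 5.6 adds: "Data at each visit will be collected by the research practitioner". Section 6.5 lists among the research practitioner's duties: "Collecting data at study visit (Visit 2, 3, 4) regarding AE, AR, and SAE".

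**Cues to allocation.** For the electrode sites, Section 5 says: "The therapist will mark this spot on the skin with a permanent marker for future sessions". The training text in the same section has the mark renewed when it fades. The trial flow chart places this in the Visit 3 box, next to the outcome measures: "SNMES group return stimulators". Appendix 1 schedules checks for skin irritation, fatigue, soreness and pain at Visits 2 and 3.

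**Safeguards stated.** Section 5.4 asks participants not to reveal their group. It has the assessor record any unblinding under disclosed, observed equipment or other, and it takes an allocation guess with a free-text rationale at Visit 3. It says the findings will shape the blinding strategy of the definitive trial.

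**The concern.** The protocol protects the assessor at randomisation and then gives the same role tasks that can reveal allocation. Adverse-reaction questions are questions about the intervention, so a truthful SNMES participant may have to mention electrodes or stimulation to the person from whom Section 5.4 asks them to conceal their group.

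Two things are at stake. The first is the blinding assessment, which is itself a feasibility output. If allocation is revealed by a task list or by ink on the leg, the result does not show whether blinding would hold under ordinary precautions. The second is the descriptive data and standard deviations taken forward to the definitive trial. Dynamometry, MRC grading, tape circumference and tactile testing all depend on the assessor's technique or judgement.

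**Working it through.** No arithmetic applies, because the protocol gives no figure for blinding success. The check traces role, visit and procedure.

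1. **Is it the same role?** Sections 5.3 and 5.4 aim to blind the research practitioner. Sections 5 and 5.6 have that role assess and collect data at each visit, and Section 6.5 has it collect AEs, ARs and SAEs at Visits 2, 3 and 4. No separate unblinded collector is named. The conflict is one of role; the protocol does not say whether one individual does everything.

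2. **Are the safety questions informative about allocation?** Section 6.1.1 lists skin reactions from electrodes or the brace, together with soreness, spasm, fatigue, strain and joint pain. Section 5 issues electrodes and study braces only to SNMES participants, so the skin items point to allocation. The others can occur in either arm and reveal little.

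3. **Would the assessor see the marks?** They are made on SNMES participants only and kept up during treatment. Section 5.6 has circumference measured at thigh and calf on both legs, strength tested in the thigh and calf muscles, and light touch tested on the lower limbs, all at Visits 2 and 3. The marks lie in the regions examined, and nothing is said about covering them. By Visit 4, at 6 months, they may have gone.

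4. **Does device return reach the assessor?** The flow chart puts it at Visit 3 but names no recipient. Section 5 has a research assistant work with the rehabilitation teams on tracking participants and getting the stimulator back. Exposure is possible but not stated.

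5. **Do the Appendix 1 checks reach the assessor?** Their timing matches Visits 2 and 3, but assessment of any problem is given to the research team generally.

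6. **Is an order fixed?** Nothing in the text at hand places outcome tests or the guess before safety questions, skin checks or device return. Order alone protects only the current visit: if the same person asks about reactions at Visit 2 and returns for Visit 3, the knowledge comes too. The 10 Metre Walk Test, the intended definitive primary outcome, is measured only at Visits 3 and 4, after that exposure may have occurred.

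7. **Would the log separate the causes?** Neither skin marks nor adverse-reaction questioning has its own category. Both would go under other, and some reaction-related unblinding would probably be recorded as disclosure.

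**The case against.** The strongest reply is that the protocol promises an effort at blinding, not success. It expects some failures, records them with their cause, and means to learn from them. The other category and the free text can capture marks or safety questions. This stands in part, but recording a failure does not prevent it, and broad categories make it harder to separate avoidable causes from unavoidable ones.

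A second reply is that the consequence is small. Section 7.3 rules out statistical comparisons between arms, and the Table 3 progression criteria concern recruitment, incomplete follow-up and adherence. This stands, and it limits the point to the blinding evidence and the descriptive data. The walk test is timed, so it is probably less open to assessor influence than manual grading.

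A third is that the order of steps may be set elsewhere. Sections 5.5 and 5.6 refer to an Appendix 3 on conducting the assessments, which is not in the text available. It could settle the order. It would not by itself change the assignment of duties in Section 6.5.

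A reader might go further and infer that these procedures certainly unblind the assessor, or that all 30 planned SNMES participants will be revealed. The document does not support this. Unblinding is an inference, the recipient of the stimulator is not stated, the Appendix 1 checks are not assigned to the blinded role, and several listed events are common to both arms. Any percentage of correct guesses would rest on an assumed fraction revealed.

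**Conclusion.** The concern holds as an internal inconsistency that should be corrected. Two elements are firm on the text: Section 6.5 gives adverse-reaction collection to the role that Section 5.4 tries to blind, and maintained SNMES-only marks lie on the limbs that role measures, with no stated mitigation. Stimulator return at Visit 3 is a third possible route that the protocol leaves open.

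The risk applies to the SNMES arm, planned at 30 of 60 participants, and is greatest at Visits 2 and 3. Thirty is the number exposed to the procedures, not an estimate of the number revealed. Carry-over to Visit 4 assumes that the same individual assesses again, which the protocol does not say. The harm is a less interpretable blinding result and possible bias, of unknown size and direction, in assessor-dependent summaries and the standard deviations drawn from them. No efficacy inference and no progression criterion is directly affected.

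**What to change.** Reconcile Sections 5.4, 5.6 and 6.5, Appendix 1 and the flow chart as follows. The content and timing of the safety checks stay as they are; only who does them and in what order changes.

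- **Order.** At each visit complete the outcome tests, and at Visit 3 the guess, before any AE or AR questions or skin checks.
- **People.** Where feasible, have existing unblinded staff collect AE and AR data. The PI is an obvious candidate: Section 6.5 already has the PI checking for SAEs at visits, and Section 5.3 names the PI among those who randomise. For home visits the questions can be asked by telephone. A skin check needing attendance then comes last.
- **Devices.** Return stimulators outside the assessment, through the research assistant who already tracks them.
- **Marks.** Cover them during assessments where the test allows. Circumference and tactile testing may not always permit it.
- **Log.** Add skin marks and adverse-reaction questioning to the recorded causes of unblinding.

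The cost is some coordination at visits and edits to the visit instructions. Sample size, outcomes and visit schedule are unchanged. Equipment seen in the home will remain a source of unblinding, and the log should then show it separately from the avoidable routes.
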